#### 10.9.2. Prohibited Therapies during treatment with IMP

Concomitant systemic or local anti-cancer medications or treatments are prohibited in this study while receiving nivolumab and/or ipilimumab treatments. Patients may not use any of the following therapies during the study:

- Any non-study anti-cancer agent (investigational or non-investigational)
- Any other investigational agents

- Anti-PD-1 / PD-L1 immune check-point blockers (except for nivolumab)
- Immunosuppressive agents
- Chronic systemic corticosteroids (more than prednisone 10 mg/day continuous or equivalent)

### **10.10. Pregnancy prevention**

Female patients who are not of childbearing potential due to being postmenopausal (1 year without menstruations without an alternative medical cause or at least 2 years without menstruation following chemotherapy) or surgically sterilised (oophorectomy, hysterectomy and/or tubal ligation) do not need to use contraception to be eligible for the trial. All other patients are considered to be of childbearing potential.

Women of childbearing potential and sexually active men must use highly effective contraception during treatment with nivolumab and ipilimumab and until 12 months thereafter. The following contraception methods are considered highly effective:

- Hormonal (estrogen and progesterone) contraception (oral, intravaginal, transdermal) associated with inhibition of ovulation
- Progesteron-only hormonal contraception (oral, injectable, implantable) associated with inhibition of ovulation
- Intrauterine deviced (IUD) or intrauterine hormone releasing systems (IUS)
- Bilateral tubal occlusion
- Vasectomised partner

Women who become pregnant while participating in the trial must discontinue trial medication immediately. The pregnancy must be reported following procedures detailed in section 12.9. Also any pregnancy that occurs in a female partner of a male study participant must be reported.

### **10.11. Treatment duration**

Patients remain on treatment until one of the following events, whichever occurs first:

- Documented progression according to RECIST v1.1 in chemo-radiotherapy phase
- Documented progression according to RECIST v1.1 in randomised consolidation phase
- Secondary malignancy resulting in need of systemic treatment
- Unacceptable toxicity
- Medical condition that prevents further treatment
- Patient withdraws consent
- Patient becomes pregnant

- One year of maintenance treatment has been completed

Nivolumab and ipilimumab are expected to trigger immune-mediated responses, which require activation of the immune system prior to the observation of clinical responses. Such immune activation may take weeks to months to be evident. Some patients may have objective volume increase of SCLC tumour lesions within 9 weeks following the start of nivolumab and ipilimumab dosing. In some patients, tumour volume or other disease parameter increases may represent infiltration of lymphocytes into the original tumour or blood. In conventional studies, such tumour volume or relevant laboratory parameter increases during the first 9 weeks of the study would constitute PD and lead to discontinuation of imaging to detect response, thus disregarding the potential for subsequent immune-mediated clinical response.

Therefore, patients with tumour volume increase detected up to week 9 of IMP treatment but without appearance of new lesions or rapid clinical deterioration should continue to be treated with IMPs and be clinically observed with a stringent imaging schedule 4 weeks later to allow detection of a subsequent tumour response. This will improve the overall assessment of the clinical activity of IMPs and more likely capture its true potential to induce clinical responses. This must follow the definitions below:

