|---------------------------|---------------------------|----------------------------|--|
| - up to 18 months: | every 9 weeks             | weeks after randomisation: | 9, 18, 27, 36, 45, 54, 63, 72, 81 (+/- 1 week) |
| - up to 2 years:   | every 12 weeks            | “                          | 93, 105 (+/- 1 week)                           |
| - years 3 and 4:   | every 6 months (26 weeks) | “                          | 131, 157, 183, 209 (+/- 1 week)                |
| - at 5 years:      |                           | “                          | 260 (+/- 1 week)                               |
- In case of clinical suspicion of distant metastases, immediate adequate diagnostic procedures including CT-scan, whole body PET-CT, bone scans and MRI (as appropriate) should be used.  
Early progression at 9 weeks: Patients with tumour volume increase documented by CT scan 9 weeks after randomisation, but without appearance of new lesions or rapid clinical deterioration should continue to be treated with IMP and clinically observed with a stringent imaging schedule 4 weeks later to determine whether there has been a decrease in the tumour size or disease stabilisation, or alternatively continued PD which would terminate the trial treatment.  
Patients who discontinue study treatment for reasons other than progressive disease: Restaging should be repeated at time of discontinuation, except if already performed within 6 weeks prior to the last dose of study treatment.
- 14 **Adverse events:** All adverse events that occur within 100 days of the last administered study medication or within 100 days after the last visit in the observation arm must be documented. Symptoms present at baseline and at randomisation will be recorded on the adverse event forms as well.
- 15 **Thoracic radiation** will be administered concurrently to chemotherapy and should preferentially start at the same time as the first chemotherapy cycle (e.g. day 1 of cycle 1), if the patient can be enrolled before chemotherapy start. Otherwise, radiotherapy should optimally start at day 1 of cycle 2, i.e. in treatment week 4. As a latest start of radiotherapy day 1 of cycle 3 is allowed, but should be exceptional.

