#### 10.11.1. Treatment beyond disease progression

Accumulating evidence indicates a minority of patients treated with immunotherapy may derive clinical benefit despite initial evidence of PD.

The assessment of clinical benefit should take into account whether the patient is clinically deteriorating and unlikely to receive further benefit from continued treatment.

Patients should discontinue study therapy upon evidence of further progression, defined as an additional 10% or greater increase in tumour burden volume from time of initial progression (including all target lesions and new measurable lesions).

New lesions are considered measurable at the time of initial progression if the longest diameter is at least 10 mm (except for pathological lymph nodes, which must have a short axis of at least 15 mm). Any new lesion considered non-measurable at the time of initial progression may become measurable and therefore included in the tumour burden measurement if the longest diameter increases to at least 10 mm (except for pathological lymph nodes, which must have an increase in short axis to at least 15 mm).

Patients treated with IMPs will be permitted to continue treatment beyond initial RECIST 1.1 defined PD – at 9 weeks CT scan assessment – if they meet all of the following criteria:

1. Investigator-assessed clinical benefit, and do not have rapid disease progression
2. Continue to meet all other study protocol eligibility criteria
3. Tolerance of study drug
4. Stable performance status
5. Only local progressive disease of known LD SCLC (absence of new lesion)

After the 9 week scan, a radiographic assessment / scan should be performed at least 4 weeks after the original PD scan to determine whether there has been a decrease in the tumour size or disease stabilisation, or alternatively continued PD which would terminate the trial treatment.

If the IMPs have been stopped for any reason, the patient enters the follow-up phase of the trial. Patients who discontinue trial treatment should be assessed by the investigator who must document the case on the appropriate eCRF.

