#### After randomisation:

For both treatment arms, post randomisation CT scans of thorax and upper abdomen will be repeated according to the schedule indicated below, until tumour progression:

- up to 18 months: every 9 weeks 9, 18, 27, 36, 45, 54, 63, 72, 81 (+/- 1 week)
- up to 2 years: every 12 weeks 93, 105 (+/- 1 week)
- years 3 and 4: every 6 months (26 weeks) 131, 157, 183, 209 (+/- 1 week)
- at 5 years: 260 (+/- 1 week)

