### 13.4. Determination of best overall response

Best overall response is defined as best response across all time points. Confirmation of partial or complete response by an additional scan is not requested in this trial.

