### 14.3. Objective response

Objective response is defined as best overall response (CR or PR) across all assessment time-points during the period from randomisation to termination of trial treatment. Objective response to chemo-radiotherapy will be determined by tumour assessment around week 15 (see trial schedule in section 2).

Objective response to IMP treatment will be determined using RECIST 1.1 criteria (see section 13).

[figure not shown]

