2.2 Study's endpoints

2.2.1 Primary endpoint

The primary endpoint of the analysis is PFS, defined as the time from the **date of randomization** until documented progression (based on RECIST 1.1 criteria) or death, if progression is not documented. Censoring (patients without progression/death) for PFS will occur at the last tumour assessment. In the frame of a sensitivity analysis, if the last tumour assessment is «Non evaluable», censoring will occur to the more recent tumour assessment where an overall evaluable result is recorded.

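### Response rate and duration of response are not cut at first RECIST 1.1 progression, so responses after a week-9 progression can count in the experimental arm only

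*Protocol*

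**What the plan says.** **Response.** Protocol 13.4: "Best overall response is defined as best response across all time points". Protocol 14.3 takes responses "during the period from randomisation to termination of trial treatment", and SAP 2.2.2 repeats that window. None of the three stops at progression. SAP 2.2.3 runs duration of response (DoR) from the documented response to progression or death.

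**Continuation after progression.** Protocol 10.11.1: "Patients treated with IMPs will be permitted to continue treatment beyond initial RECIST 1.1 defined PD". This applies to the week-9 scan, under five conditions that include no new lesion. Footnote 13 of the trial schedule says that such a patient "should continue to be treated with IMP and clinically observed with a stringent imaging schedule 4 weeks later". Section 10.11 gives the motive: "In conventional studies, such tumour volume or relevant laboratory parameter increases during the first 9 weeks of the study would constitute PD". That sentence goes on to say that imaging for response would then stop. The same section lists, among the events that end treatment, "Documented progression according to RECIST v1.1 in randomised consolidation phase".

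**Observation arm.** Patients enter follow-up at progression (Protocol 16.6). In both arms, scheduled CTs "will be repeated according to the schedule indicated below, until tumour progression" (Protocol 13.2).

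**PFS.** SAP 2.2.1 counts time "until documented progression (based on RECIST 1.1 criteria) or death, if progression is not documented", as read by the local radiologist (SAP 1.1).

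**The concern.** The response window is tied to treatment, and only one arm has treatment. An experimental patient can progress at week 9, stay on treatment, shrink later and be counted as a responder. An observation patient with the same week-9 scan leaves the scheduled CTs and has no stated route to a later response. The response rate then compares different observation periods in the two arms, and the extra time favours the experimental arm.

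DoR fails for the same patients. Their first progression comes before their response, and no rule says which later progression ends the duration.

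Immune-related response is planned only as an exploratory, post-hoc, central review (Protocol 13.1 and 18.4). Responses after progression belong there rather than in the RECIST 1.1 rate.

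**Working it through.** **1. One patient through the rules.** Take local growth that meets RECIST 1.1 progression at week 9, with no new lesion, and partial response at week 18.
- *Experimental arm.* PFS: event at week 9. Best response: partial response at week 18, because treatment has not ended. DoR: starts at week 18, after the progression, so its end is undefined.
- *Observation arm.* PFS: event at week 9. The patient enters follow-up and scheduled CTs stop. Best response: progression.

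**2. The window end.** The observation arm has no treatment to terminate. Protocol 16.1.4 gives it an end-of-treatment visit at progression or 15 months, but 14.3 does not use that visit as the window end. In the experimental arm an early stop for toxicity closes the window, although CTs continue (Protocol 16.9). The windows therefore differ in more than one way.

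**3. The plan's own figure.** Inputs from SAP 1.4.2 and section 3: medians 13.1 and 22.8 months, one-sided 0.05, 80% power, 81 events.
d = 4(1.645 + 0.842)² / [ln(13.1/22.8)]² = 24.73 / 0.307 = 80.5, so 81. With the HR rounded to 0.57 the formula gives 79. The 81 reproduces, and the fix does not change it.

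**4. How many patients.** Exponential PFS; 9 weeks = 9 × 7 / 30.4375 = 2.07 months.
- Median 22.8: 1 − 2^(−2.07/22.8) = 6.1%.
- Median 13.1 (no effect): 1 − 2^(−2.07/13.1) = 10.4%.

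The number randomised after closure is not in the documents; 120 to 200 is assumed, so 60 to 100 in the experimental arm. That gives 3.7 to 6.1 week-9 events at the design median, or 6.2 to 10.4 with no effect. If 25–50% are local growth only (assumed), 0.9 to 3.0 patients take the route at the design median, or 1.6 to 5.2 with no effect.

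If every one of them later responded, the experimental response rate would rise by 0.061 × 0.25 = 1.5 to 0.061 × 0.50 = 3.0 points, or by 2.6 to 5.2 points at the 10.4% rate. Patients with complete response during chemo-radiotherapy are excluded from the response rate (SAP 2.2.2), so the rise is larger if early progression is concentrated in the rest.

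**5. PFS, if sites did not count the week-9 scan.** Simulated with no true effect: exponential PFS with median 13.1 months, events detected on the protocol's CT grid, 36-month uniform accrual, analysis at event 81, unstratified log-rank, one-sided 0.05, 4,000 runs per cell (Monte Carlo standard error about 0.3 points). Rejection rates:

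| Experimental week-9 events | N=120 | N=150 | N=200 |
|---|---|---|---|
| All counted at week 9 | 5.8% | 5.2% | 5.0% |
| All redated to week 13 | 5.8% | 6.1% | 5.9% |
| 25% recorded as non-progression | 7.5% | 7.4% | 8.3% |
| 50% recorded as non-progression | 10.6% | 12.0% | 12.6% |
| 50% so recorded, the rest redated | 10.2% | 12.8% | 14.1% |

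The mean null HR falls to between 0.954 and 0.942 in the 25% row and between 0.912 and 0.885 in the 50% row. A separate set of 2,000 runs per setting (120 to 180 randomised) took 25–50% of week-9 events as going down this route: 5.7–9.2% if half of those are recorded as non-progression, and 7.7–11.7% if all are.

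**The case against.** **The exception is narrow.** RECIST progression otherwise ends treatment (Protocol 10.11 and 19.2), so for most patients the end of treatment and progression coincide. Response rate is a secondary endpoint with no multiplicity adjustment. This stands, and it keeps the effect small. It does not make the written rule equal between the arms.

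**Observation patients may be rescanned too.** The rescan sentence in Protocol 16.6 sits in a note that opens with both arms. That is a real ambiguity, but the sentence ends with stopping trial treatment, and only the experimental arm has a stated way to continue. It does not give the observation arm a response window.

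**A reader might infer that PFS follows a different event rule in each arm and that type I error is inflated.** The remark about conventional studies invites this, and neither PFS definition says first progression or addresses continued treatment. The documents do not support it. The remark sits in a section on treatment duration and leads to a point about stopping imaging. Section 10.11.1 itself labels the week-9 scan RECIST 1.1 progression. Table 15 makes target-lesion progression an overall progression with no confirmation step. SAP 2.2.1 ties PFS to RECIST 1.1, and immune-related criteria are exploratory only. The plain reading dates PFS at week 9 in both arms.

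Nor do the two harms add up in one patient. If the week-9 scan is a PFS event, only response rate and DoR are affected; if it is recorded as non-progression, a later response is not a post-progression response.

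**Conclusion.** The point holds for response rate and DoR, on the documents' own definitions: followed as written, they count responses after progression in one arm and leave DoR undefined for those patients. The size is modest, at most 1.5 to 3.0 percentage points on the experimental response rate at the design median (2.6 to 5.2 with no effect), assuming a 25–50% local-only share and a later response in every such patient.

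For PFS the documents need a clarification, not a correction. Type I error of about 6–12% (14.1% in the most extreme run) is a worst case: it requires sites to record as non-progression a scan that the protocol calls progression, in shares with no source in the documents. Redating to week 13 alone leaves it at about 5–6%. The clarification is still worth making, because PFS is now the sole primary endpoint and is read locally in an open-label trial.

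**What to change.** 1. **SAP 2.2.2 and 2.2.3.** Derive best response, response rate and DoR in both arms only from assessments up to and including the first RECIST 1.1 progression. Set one window end for patients without progression that works in both arms. A fixed time from randomisation would do; 15 months already marks the end of the observation period in that arm.
2. **Post-progression shrinkage.** Report it only under the planned exploratory immune-related review.
3. **SAP 2.2.1.** State that PFS is dated at the first RECIST 1.1 progression or death in both arms, whatever the later treatment or rescan shows. Check the week-9 and rescan forms against this.
4. **Reconcile the protocol text.** The passages that end treatment at progression (10.11, 19.2), the continuation text (trial schedule footnote 13, 10.11, 10.11.1) and the rescan note in 16.6 must be made consistent, including which arms are rescanned. Week 9 is counted from treatment in 10.11 but from randomisation in footnote 13 and 16.6, and treatment may start up to 14 days after randomisation.

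**Cost.** A few SAP sentences, a small programming change and one data check, plus the protocol reconciliation. With accrual closed, the SAP is the practical place for the endpoint rules. The 81 events are unchanged. The downside is that genuine late responses after pseudo-progression leave the RECIST 1.1 response rate; they remain visible in the exploratory review.

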#### 10.11.1. Treatment beyond disease progression

Accumulating evidence indicates a minority of patients treated with immunotherapy may derive clinical benefit despite initial evidence of PD.

The assessment of clinical benefit should take into account whether the patient is clinically deteriorating and unlikely to receive further benefit from continued treatment.

Patients should discontinue study therapy upon evidence of further progression, defined as an additional 10% or greater increase in tumour burden volume from time of initial progression (including all target lesions and new measurable lesions).

New lesions are considered measurable at the time of initial progression if the longest diameter is at least 10 mm (except for pathological lymph nodes, which must have a short axis of at least 15 mm). Any new lesion considered non-measurable at the time of initial progression may become measurable and therefore included in the tumour burden measurement if the longest diameter increases to at least 10 mm (except for pathological lymph nodes, which must have an increase in short axis to at least 15 mm).

Patients treated with IMPs will be permitted to continue treatment beyond initial RECIST 1.1 defined PD – at 9 weeks CT scan assessment – if they meet all of the following criteria:

1. Investigator-assessed clinical benefit, and do not have rapid disease progression
2. Continue to meet all other study protocol eligibility criteria
3. Tolerance of study drug
4. Stable performance status
5. Only local progressive disease of known LD SCLC (absence of new lesion)

After the 9 week scan, a radiographic assessment / scan should be performed at least 4 weeks after the original PD scan to determine whether there has been a decrease in the tumour size or disease stabilisation, or alternatively continued PD which would terminate the trial treatment.

If the IMPs have been stopped for any reason, the patient enters the follow-up phase of the trial. Patients who discontinue trial treatment should be assessed by the investigator who must document the case on the appropriate eCRF.

## 11. Safety of Investigational Medicinal Products

Please note that both nivolumab and ipilimumab are considered as Investigational Medicinal Product (IMP). Cisplatin, carboplatin and etoposide constitute the required chemotherapy, but are not investigational.

### 11.1. Ipilimumab

#### 11.1.1. Safety profile of ipilimumab

The safety profile of ipilimumab at a dose of 10 mg/kg was characterised in a total of 325 patients who received multiple doses of 10 mg/kg ipilimumab as monotherapy in the 4 completed melanoma studies (CA184004, -007, -008, and -022). Overall, the incidence of Grade 3/4 AEs attributable to study drug was 31%. The target organ system, the incidence and the severity of the most commonly observed irAEs are displayed in Table 11.

**Table 11: Summary of irAE safety data for 10 mg/kg ipilimumab in melanoma**

	Total (%)	Low-grade (Grade 1 - 2) (%)	High-grade (Grade 3 - 4) (%)	Median Time to Resolution of Grade 2 - 4 irAEs (weeks)
All irAEs	72.3	46.2	25.2	-
Skin (eg, rash, pruritus)	52.0	49.2	2.8	6.14
GI (eg, colitis, diarrhoea)	37.2	24.9	12.3	2.29
Liver (eg, LFT elevations)	8.0	0.9	6.8	4.0
Endocrine (eg, hypophysitis, hypothyroid)	6.2	3.7	2.5	20.1

Overall, the 10 mg/kg had an acceptable safety regimen, while being the most active dose. The study drug-related deaths across the program are in section 5 of the IB.

Across clinical studies that utilised ipilimumab doses ranging from 0.3 to 10 mg/kg, the following adverse reactions were also reported (incidence less than 1% unless otherwise noted): urticaria (2%), large intestinal ulcer, oesophagitis, acute respiratory distress syndrome, renal failure, and infusion reaction.

Based on the experience in the entire clinical program for melanoma, the incidence and severity of enterocolitis and hepatitis appear to be dose dependent.

#### 11.1.2. Immunogenicity

In clinical studies, 1.1% of 1024 evaluable patients tested positive for binding antibodies against ipilimumab in an electrochemiluminescent (ECL) based assay. This assay has substantial limitations in detecting anti-ipilimumab antibodies in the presence of ipilimumab. Infusion-related or peri-infusional reactions consistent with hypersensitivity or anaphylaxis were not reported in these 11 patients nor were neutralising antibodies against ipilimumab detected.

Because trough levels of ipilimumab interfere with the ECL assay results, a subset analysis was performed in the dose cohort with the lowest trough levels. In this analysis, 6.9% of 58 evaluable patients, who were treated with 0.3 mg/kg dose, tested positive for binding antibodies against ipilimumab.

Immunogenicity assay results are highly dependent on several factors including assay sensitivity and specificity, assay methodology, sample handling, timing of sample collection, concomitant medications, and underlying disease. For these reasons, comparison of incidence of antibodies to ipilimumab with the incidences of antibodies to other products may be misleading.

